### **5.3 Subject Withdrawal**

Subjects are free to withdraw from participation in the study at any time upon request.

An investigator may terminate a study subject's participation in the study if:

- Any clinical adverse event (AE), laboratory abnormality, or other medical condition or situation occurs such that continued participation in the study would not be in the best interest of the subject.
- The subject meets an exclusion criterion (either newly developed or not previously recognized) that precludes further study participation.

### **5.4 Premature Termination or Suspension of Study**

This study may be suspended or prematurely terminated if there is sufficient reasonable cause. Written notification, documenting the reason for study suspension or termination, will be provided by the suspending or terminating party. If the study is prematurely terminated or suspended, the principal investigator will promptly inform the IRB and will provide the reason(s) for suspension or termination. Circumstances that may warrant termination include, but are not limited to:

- Early attainment of statistical significance;
- Continuation of enrollment due to positive trend; and
- Determination of unexpected, significant, or unacceptable risk to subjects.
- Insufficient adherence to protocol requirements.
- Data that are not sufficiently complete and/or evaluable.
- Determination of futility.

### **5.5 Costs to Subjects**

All research related procedures and/or medications will be provided at no charge to the subject and will not be billed to the insurance carrier.

## 6 STUDY SCHEDULE

### 6.1 Screening Visit (Day -28 to -1)

- Obtain and document consent from potential participant on the consent form.
- Review medical/dental history to determine eligibility based on inclusion/exclusion criteria.
- Review medications history to determine eligibility based on inclusion/exclusion criteria.
- Perform medical/dental examinations as needed to determine eligibility.
- Schedule study visits for individuals who are eligible and available for the duration of the study.
- Provide potential participants with instructions needed to prepare for first study visit.

### 6.2 Enrollment/Baseline Visit (Visit 1, Day 0)

- Review and confirm informed consent.
- Verify inclusion/exclusion criteria.
- Update any changes in demographic information, medical/dental history, medication history, alcohol and tobacco use history.
- Record results of physical and dental examinations.
- Collect blood/urine/saliva/other specimen.
- A single blood sample will be collected via antecubital venipuncture by a phlebotomist prior to MR imaging, 10-15 ml blood collected. The blood sample will be collected after verification of negative urine pregnancy test in women of childbearing potential.
- All patients will undergo a comprehensive baseline clinical assessment including evaluation of their cardiovascular risk factor profile. The specific information that will be collected is seen in the table below.

Table 2: Clinical Assessment Parameters to be Collected

Demographics	Antecedent CV Hx & Risk Factors	Clinical Parameters	Current Medications	Clinical Biochemistry	Ultrasound Findings
Age-Years Sex-% male Race Body Mass Index – kg/m  Alcohol use Tobacco Use	Smoking T2D Hypertension Hypercholesterolemia	Heart Rate Systolic BP Diastolic BP Ankle-brachial index	Aspirin Clopidogrel Statin blocker ACE/ARI Calcium channel blocker Other anti-hypertensives Oral nitrates	Total Cholesterol HDL-C, LDL-C VLDL Triglycerides Creatinine BUN AST ALT Bilirubin hsCRP Uric Acid Salivary cortisol	Thickness of anterior and distal wall of artery with lesion. Assessment of flow restriction

### 6.3 Imaging Visit (Day 0-29)

- Subjects, meeting inclusion and exclusion criteria, will be contacted by research assistant or physician in person or by telephone to complete pre-MRI consent screening by use of the MRI safety checklist. After confirming consent to study protocol, those willing to participate will be scheduled to a 1-hour time-slot to appear at the Department of Radiology to undergo an MRI.
- At the appointed time, subjects will be met by a research assistant or physician and will be oriented. Consent will be confirmed both for the MR imaging as well as the pathology specimen (carotid endarterectomy specimen after surgery in carotid artery patients and peripheral arterial specimen in PAD patients) and the MRI safety checklist repeated. Subjects will change into hospital scrubs (provided) and remove any jewelry, watches, etc.
- The subject should be asked if he or she had a permanent coloring technique (i.e., tattooing) applied to any part of the body. This includes cosmetic applications such as eyeliner, lip-liner, lip coloring, as well as decorative designs.
- The subject should be informed of the risks associated with the site of the tattoo.
- The subject should be advised to immediately inform the MRI technologist regarding any unusual sensation felt at the site of the tattoo in association with the MR procedure.
- As a precautionary measure, a cold compress (e.g., ice bag) may be applied to the tattoo site during the MR procedure.
- Women of childbearing potential will be asked to provide a urine sample for a urine pregnancy test before each MRI study. If the test is negative, the patient may continue to participate. A positive pregnancy test will exclude further participation.
- Subjects will then be escorted by a research assistant/ physician into the MRI scan room and asked to lie on the imaging table. The patient will undergo MRI imaging of the specific arterial target, which is to include post-gadolinium contrast enhanced images. The total scan duration will be less than 60 minutes. All equipment for monitoring (ECG and respiration) and imaging is approved for human clinical use.

**Table 3: Image acquisition sequences used in the protocol**

Contrast	T1	T2	TOF	Gadolinium	Diffusion	Phase Contrast
Imaging Sequence	BB 2D-TSE or FAST SE	T2 weighting 2D-TSE or FAST SE	MRA T1-FFE or FLASH or SPGR	DCE T1-TFE THRIVE or VIBE or FGRE	DWI SE-EPI	Q-flow T1-FFE or FLASH or SPGR
Acquisition	Before and after contrast inf; Fat Sat	Long TR, long TE; Fat Sat; inflow suppression	Fat Sat; inflow suppression	T1 weighted; Fat Sat	B values at 0, 500, and 1000 s/mm 	Choosing in phase and out of phase TEs

[figure not shown]
- **Carotid Artery.** All carotid MR axial image acquisitions will have a FOV of maximum 140×120mm, a slice thickness of maximum 4mm, and an acquisition matrix of at least 280×256, and a longitudinal coverage of at least 30mm. The MR imaging will be centered on the bifurcation of the symptomatic carotid arteries, defined as the arteries responsible for the neurological symptoms.
- **Femoral Artery:** The femoral artery will be scanned employing a standard leg coil placed around the thigh and conventional prospective ECG triggering. All femoral MR axial image acquisitions will have a FOV of maximum 140×120mm, a slice thickness of maximum 4mm, and an acquisition matrix of at least 280×256, and a longitudinal coverage of at least 15 cm. The MR imaging will start at the femoral bifurcation and continuing through the adductor canal.

Gadolinium intravenous injection (0.1mmol/kg) will take place in between the MRI scans while the subject is lying in the scanner. A physician will be present at all times. During the imaging procedure, subjects will be monitored physiologically by the ECG and respiration monitoring devices, and also observed by closed circuit television. Further, they will have an attached emergency call button in-hand to activate voice communication. Following completion of the imaging study, subjects will be excused and their participation in the study complete.

#### 6.4 Histopathology for Patients Undergoing Surgery within 30 Days of MRI

At the time of surgical excision, a suture will be placed at the anterior aspect of the proximal end (closest to the heart) of each endarterectomy specimen and at least 1 additional suture placed on the anterior aspect of the specimen to allow for proper orientation of the specimen during embedding and sectioning of the specimen so that the sections obtained can be aligned with the MR images. After endarterectomy during surgery, the excised plaque specimens will be sent to the hospital's pathology lab to be analyzed by two board-certified pathologists. Established hospital histopathology protocols will be used for the histology processing. The specimens will be fixed in standard fashion in 10% buffered neutral formalin, decalcified, and then processed routinely to obtain paraffin blocks. Samples will be step-sectioned to obtain four (10  $\mu$ m thick) sections every 2.0 mm throughout the length of the endarterectomy specimen and stained (Hematoxylin-Eosin, Masson's trichrome, Verhoeff van Gieson and Picosirius red). The H&E and Masson's Trichrome will be used to identify morphological and structural features for categorizing according to the proposed modified AHA classification scheme [8]. Picosirius Red Staining is used to identify demarcations of the connective tissue and the extent and type of fibrotic tissue (collagen) present in the intimal regions of the lesions [9]. The sections will be stained with Masson's trichrome (Sigma Aldrich) for cellular components [SMC-pink, red blood cells (RBC)-red], fibrous tissue (blue), fibrin and platelet-rich thrombus (deep purple). Picosirius red (Electron Microscopy Sciences, Hatfield, PA) staining is used to identify the type of collagen fibers (type I-old fibers stain yellow-orange and type III-new fibers stain green). The Verhoeff's van Giesen stained sections will be used to identify the internal (IEL) and external elastic laminae (EEL) which delineate the boundaries of the intima and media (IEL) and the media and adventitia. The lipid core is evaluated by use of all four sections, and defined as the negative staining area that may contain inflammatory cells, collagen and elastin fibers. The presence and area of classic cholesterol clefts will also be assessed. Atherosclerotic plaques will be categorized into early (types II and III) and advanced (types IV, Va, Vc and VI) plaques according to a proposed modified American Heart Association (AHA) classification. Type VI plaques were further subdivided into VI-ruptured and VI-eroded to discriminate whether thrombi were associated with demarcation of the endothelial layer of the intima or not. Rupture was defined as a discontinuity of the endothelium resulting in a contact of the thrombus with the underlying lipid core. Erosion was identified when the thrombus is attached to an intima that lacked endothelium and an underlying myointimal region that is rich in SMC and proteoglycans. Plaques types VII (calcification) and VIII (fibrotic) are proposed as two forms of regression of

plaques that may be associated with intensive lipid lowering drug regimens [10]. Calcification and fibrosis will be identified with the H&E and Masson's Trichrome stains.

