**Table 1: Analytes interrogated by vascuCAP™, understood as a multiplex assay**

Analyte	Description	Type and Units	Truth Standard
Lipid Core	Distinguished by presence of lipids, intermixed with extracellular matrix fibers, and/or necrotic tissue.	Expressed by burden in mm  and categorical variables for degree and uniformity using a 0/1/2 scale.	Histopathology considered as ground truth.
Fibrosis	Intimal presence of dense, homogeneous/organized collagen extracellular matrix with smooth muscle cells/fibroblasts embedded therein, but no appreciable lipid or necrotic tissue.	Expressed by volume in mm  and categorical variables for degree and uniformity using a 0/1/2 scale.	Histopathology considered as ground truth.
Intra-plaque hemorrhage	Presence of erythrocytes in the deeper regions of the plaque, with or without communication to the lumen or neovasculature.	Expressed by burden in mm  and confidence in %.	Histopathology considered as ground truth.
Inflammation	Accumulations of macrophages and lymphocytes in the deeper regions of the plaque that may bridge the neointima, and the media of the vessel	Expressed by burden in mm  and categorical variables for degree and uniformity using a 0/1/2 scale.	Histopathology considered as ground truth.
Vascular Leak	Composed of endothelial permeability, neovascularization, necrosis, and collagen breakdown.)	Expressed by distribution volume in mm  and categorical variables for degree and uniformity using a 0/1/2 scale.	Histopathology considered as ground truth.
Calcification	Intimal/medial presence of calcification with osteoblasts present therein, but	Expressed by burden in mm  and categorical variables for	Histopathology considered as

Analyte	Description	Type and Units	Truth Standard
	containing no appreciable lipid or necrotic tissue.	degree and uniformity using a 0/1/2 scale.	ground truth.
Remodeling Ratio	Calculated as the ratio of vessel area with plaque to reference vessel wall area without plaque	Expressed with value less than 1 for inward remodeling and greater than 1 for outward remodeling	Calculations from manual contour by radiologist as an imperfect(subjective) reference standard

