### 8.1 Aim I

The first study aim is to estimate the bias and precision of each of the following functional analytes, which will be measured for each target lesion by both vascuCAP™ and histopathology:

- a. Plaque lipid
- b. Plaque fibrosis
- c. Plaque inflammation
- d. Intra-plaque hemorrhage burden and confidence.
- e. Plaque vascular leak
- f. Calcification

For each of these functional analytes, three measurements will be evaluated for a total of 18 measurements per target lesion: volume in mm^3, and degree and uniformity both measured on a three-point ordinal scale. The same measurements will be taken via histopathology, where the volume of each analyte will be measured using the same units (i.e. mm^3); however, degree and uniformity are graded subjectively on histopathology by the pathologist.

We anticipate that each patient will have at least one target lesion and some patients, especially the PAD patients, will have two target lesions, on average. There will be no replicate measurements (i.e. all of the measurements are obtained objectively by the algorithm so multiple runs should not produce different results).

For volume measurements for each analyte for each site (i.e. neck and leg), we will plot the value measured by histopathology vs. the difference between the value measured by vascuCAP™ and the value measured by histopathology. Any analyte not measurable will also be indicated on the plot using a different plotting character. The resulting plot will be inspected visually for the following:

1. Limits of vascuCAP™'s quantitation;
2. Associations between the magnitude of the histopathology measurement and bias; and
3. Associations between the magnitude of the histopathology measurements and heteroscedasticity in the vascuCAP™ measurements.

If the plots of carotid and femoral endarterectomies have similar distributions, then the data from these sites will be pooled; otherwise, separate analyses will be performed.

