A linear model will be fit (for all of the data or for a subset of histopathology values, depending on the findings from the plot) where the dependent variable is the vascuCAP™ measurement ( $X$ ) and the independent variable is the histopathology value ( $Y$ ). Generalized estimating equations (GEEs) (to account for the fact that some patients will have more than one target lesion) will be used to estimate the linear function:  $E(Y|X) = \beta_0 + \beta_1 X$ . An unstructured working covariance will be used. We will construct a 95% CI for the intercept  $\beta_0$  using a t-statistic as the pivotal statistic. CIs not containing 0 indicate fixed bias. We will also construct a 95% CI for the slope  $\beta_1$ . CIs not containing 1 indicate proportional bias [11].

The precision of the vascuCAP™ measurements will be estimated by the standard deviation:

$$\sqrt{\frac{1}{n-1} \sum_{i=1}^n (Y_i - X_i - \bar{d})^2} \text{ where } \bar{d} \text{ is the sample mean of the differences, } \bar{d} = \frac{1}{n} \sum_{i=1}^n (Y_i - X_i) \text{ [1].}$$

We will construct a 95% CI for the precision using bootstrap methods.

We will plot the bias profile (plot of bias of measurements for various ranges of histopathology values vs. the histopathology value) and precision profile (plot of standard deviation of vascuCAP™ measurements from patients with similar histopathology values vs. the histopathology value) as visual summaries of vascuCAP™ performance for the bias and precision components, respectively [12].

In addition to reporting these technical performance characteristics of the volume measurements, we will also report i) the coverage probability (CP) and ii) a discrimination index [11]. The CP is the probability that the absolute difference between the value measured by vascuCAP™ and the value measured by histology is less than  $d_0$ , i.e.  $\pi = \Pr(|Y - X| < d_0)$ . We will plot the CP for a range of values for  $d_0$ . The discrimination ability of the measurements, i.e. the ability of vascuCAP™ to discriminate between different magnitudes of histopathology values, will be measured using the area under the ROC curve for continuous measures [13]. 95% CIs for the CP and ROC area will be constructed using methods for clustered binary data [14] and clustered ROC data [15], respectively.

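### The Aim I bias regression treats its regressor as error-free, so measurement error in that variable may be reported as fixed or proportional bias of vascuCAP, or may hide real bias

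*Combined protocol and SAP*

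**What the plan says.** Table 1 of the protocol gives the reference status for all six functional analytes: "Histopathology considered as ground truth". Section 6.4 sends the excised plaque "to be analyzed by two board-certified pathologists". It does not say whether both read every lesion, whether they read separately or by consensus, or how two volumes become one.

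Section 8.1 describes a linear model "where the dependent variable is the vascuCAP™ measurement", labelled X, and "the independent variable is the histopathology value", labelled Y. The equation displayed next is E(Y|X) = β0 + β1X, which puts histology on the outcome side. Words and equation therefore point in opposite directions.

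The fit uses GEE, and the only reason given is "to account for the fact that some patients will have more than one target lesion". Two rules follow. For the intercept: "CIs not containing 0 indicate fixed bias". For the slope: "CIs not containing 1 indicate proportional bias". No reliability term, Deming fit or sensitivity analysis for measurement error is planned. The statement in section 8.1 that there are no replicates is justified for the algorithm only.

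Section 8.2 takes a different line for Aim II. It accepts that manual contouring carries bias and measurement error, and so uses a criterion with a between-reader term.

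**The concern.** The two rules are valid only if the regressor is measured without error. Histology volumes are built up from sections taken every 2.0 mm and read by people, so some error is to be expected. In the direction given in words, classical error in histology shrinks the slope toward 0 and lifts the intercept. The plan would then attribute reading error to the device, as proportional and fixed bias together. If the true slope is above 1, the same shrinkage moves it toward 1 and can conceal real bias.

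Bias is a primary objective, and section 4 says that phase 2 supplies the definitive results for the 510(k) application. As written, the analysis cannot tell a biased device from a noisy reference.

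**Working it through.** **Inputs from section 8.1.** Mean volume 25 mm³. Precision, defined as the SD of Y − X, 10-20% of the mean (2.5 to 5.0 mm³). Within-patient correlation 0.5. Phase 2 minimum of 35 patients: 25 carotid with one lesion and 10 PAD with two, so 25 + 20 = 45 lesions.

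**The plan's own figure.** Effective size m = 0.75n + 0.25n(2/1.5) = 1.0833n, so m = 37.9 at n = 35. With t on n − 1 df, which reproduces Table 4 within 0.01, the half-width at SD 3.75 is 1.238. The total width is 2 × 1.238/25 = 9.9%, against 10% stated. That calculation concerns the mean difference. Neither it nor Table 5 addresses the slope.

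**Assumptions.** The documents give neither the reading SD nor the between-lesion SD. I took device SD 2.5 mm³ (10%), reading SD 1.25, 2.5 or 3.75 mm³ (5, 10, 15%), and between-lesion SD 5, 7.5 or 12.5 mm³ (20, 30, 50%).

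The planned precision already contains both errors, so each pair must fit the 10-20% range:
- √(2.5² + 1.25²) = 2.80, or 11%
- √(2.5² + 2.5²) = 3.54, or 14%
- √(2.5² + 3.75²) = 4.51, or 18%

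All three fit.

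**Device on histology (the words).** With true slope 1 and true intercept 0, the expected slope is λ = Var(true)/[Var(true) + Var(reading)] and the expected intercept is (1 − λ) × 25. For example, with between-lesion SD 5 and reading SD 2.5, λ = 25/(25 + 6.25) = 0.80 and the intercept is 5.0 mm³.

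False-flag rates come from simulation at 35 patients and 45 lesions. The fit was least squares with cluster-robust t intervals, as a stand-in for the planned GEE. Where repeated sets of runs differed, the range is shown. Columns are between-lesion SD.

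| Reading SD | Slope (20 / 30 / 50%) | Slope CI excludes 1 (20 / 30 / 50%) |
|---|---|---|
| none | 1.00 / 1.00 / 1.00 | 5-7% throughout |
| 5% | 0.94 / 0.97 / 0.99 | 13-15% / 10% / 7-8% |
| 10% | 0.80 / 0.90 / 0.96 | 57-60% / 33-34% / 17-18% |
| 15% | 0.64 / 0.80 / 0.92 | 94-95% / 73-76% / 37-39% |

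At reading SD 10% the intercept interval wrongly excludes 0 in about 56%, 32% and 15% of studies. More patients make it worse: at 75 patients the slope flags are 88%, 59% and 28%.

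**Masking.** With λ = 0.80, a true slope of 1.25 has expected value 1.25 × 0.80 = 1.00.

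**Histology on device (the equation).** Reading error alone now leaves the slope at 1.00, with 6-8% flagged. Device error attenuates it instead. Device SD 10% gives 0.80, 0.90 and 0.96 by the same formula. Device SD 15% with no reading error gives 0.64, 0.80 and 0.92, with 99%, 89% and 52% flagged.

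**Averaging two independent readings.** This halves the reading variance. At reading SD 10% the slopes become 0.89, 0.95 and 0.98, with 27%, 17% and 11% flagged, so averaging helps but is not enough. Correcting with the between-reader variance brings the mean slope to 1.00-1.02, but only because the simulated error is all independent between readers.

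**The case against.** The effect depends on two quantities that the documents do not give. With a reading SD of 5% and widely varying lesions it almost vanishes. This stands, and it is why the result is stated as a range.

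Section 8.1 sets no pass/fail limit on the slope. It also reports precision, bias and precision profiles, coverage probability and an ROC-type index, and zero-mean reading error leaves the mean difference unbiased. That is true, but the two rules still say what the intervals indicate about the device.

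A reader might infer that a second reading is collected and then discarded. The documents do not support this. Section 6.4 does not say that both pathologists read each lesion. The singular in "degree and uniformity are graded subjectively on histopathology by the pathologist" concerns the ordinal grades, which do not enter this regression.

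A reader might also use histology reliabilities of 0.90 and 0.80 with a volume CV of 50% and device SD 15%, and quote false flags of 37% and 76%. Those inputs imply histology SDs of 4.17 and 6.25 mm³. The difference SDs are then √(3.75² + 4.17²) = 5.61 (22%) and √(3.75² + 6.25²) = 7.29 (29%), both outside the planned 10-20%.

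Finally, the difference between readers misses error that they share: sectioning, processing and decalcification, and co-registration with MRI. This stands, and it limits what a corrected slope can prove.

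**Conclusion.** The concern holds in a limited form. The bias rules in section 8.1 assume an error-free regressor, and the plan neither justifies that nor measures the error. In the direction given in words, an unbiased device would be flagged in about 8% to 95% of phase 2 studies of 35 patients, over assumed values that fit the planned precision, against 5-7% with no reading error. This rests on classical, independent reading error and on assumed reading and between-lesion SDs. In the displayed direction, device error takes the same role, so neither version rescues the rule.

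It does not follow that vascuCAP will be declared biased, or that the slope must fall below 1. The documents support only that this may happen, and that the plan could not recognise it. The matter should be settled before phase 2 specimens are read.

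**What to change.** 1. Reconcile the X and Y labels with the equation and state the regression direction. Device on histology is the easier to correct: it needs only the reading variance, which two pathologists can supply. The reverse needs the device error variance, and no device replicates are planned.
2. State that the two pathologists already named record volumes independently, for all lesions or for a defined subset if duplicate reading of all was not intended. Use their mean where both read.
3. Estimate the reading variance from their differences, as half the mean squared difference for a single reading and half of that again for a mean of two. Report a Deming or reliability-corrected slope and intercept, with intervals, beside the planned ones.
4. Do not attribute a slope interval that excludes 1 to the device unless the corrected slope agrees. Equally, do not treat the corrected slope as sole proof of no bias. Say that the correction is a minimum, because it misses error shared by both readers.

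The cost is SAP wording, a wider interval for the corrected slope, and recording work. The recording work is modest for a subset. It is larger for all lesions if duplicate reading was never intended, since six analytes are measured at 2 mm steps.
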